All statistical analysis will be performed in the two cohorts of interest, ie, infants aged 1 month to <1 year and in patients aged 1 to <2 years, separately using the Aetion Evidence Platform version 4.2. Descriptive statistics will be presented for the key variables to characterize the overall cohort treated with IV pantoprazole and the 3 subgroups defined based on the presence or absence of GERD and EE during the baseline period or on the index date. Incidence rates of outcomes of interest will be estimated as the number of patients with a specific outcome of interest during the follow-up period divided by the total person-time at risk and reported as incidence rate per 1,000 person-years with associated 95% confidence intervals (CIs). The CIs will be estimated using the exact method for event counts less than 10, assuming a Poisson distribution. Incidence rates for all outcomes of interest will be calculated in the overall cohort and in each of the 3 subgroups. Within the overall cohort and in the 3 subgroups, incidence rates will be estimated by duration of IV pantoprazole treatment (4 days, 4 days). Two sensitivity analyses will be performed as follows: (1) analysis will be repeated in both cohorts without exclusion criteria of at least 30-day enrollment prior to the index date to test the sensitivity to enforced 30-day enrollment period, and (2) analysis will be repeated in both cohorts, stratified by those patients identified via ICD-9-CM codes versus ICD-10-CM codes, respectively to test the sensitivity to ICD-9-CM versus ICD-10-CM coding for subgroup classification.

Milestones

Study protocol is planned to be submitted to the FDA by 20 August 2021 and study report is planned to be submitted to the FDA by 30 June 2022.

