9.6. Study size

There are no a priori hypotheses specified, and therefore, sample size calculations are not applicable. All eligible patients meeting inclusion/exclusion criteria will be included in the study. Based on preliminary feasibility, it is anticipated that 7,489 infants aged 1 month to <1 year and 6,657 patients aged 1 to <2 years who have been treated with IV pantoprazole will be eligible for inclusion in the study. Table 5 below shows the 95% confidence intervals around varying hypothetical frequencies of outcomes given a 7,489 and 6,657 patient sample, calculated using the Wilson score interval.

Table 5. Precision estimates for varying frequencies of outcomes for given 7,489 and 6,657 patient samples

Sample size	Outcome Frequency	N Events*	Lower 95% Bound	Upper 95% Bound
7489	0.002	15	0.0012	0.0033
	0.005	37	0.0036	0.0068
	0.01	75	0.0080	0.0125
	0.05	374	0.0452	0.0551
	0.1	749	0.0934	0.1070
	0.2	1498	0.1911	0.2092
6657	0.002	13	0.0011	0.0033
	0.005	33	0.0035	0.0070
	0.01	67	0.0079	0.0128
	0.05	333	0.0450	0.0555

10 February 2022

0.1	666	0.0931	0.1075
0.2	1331	0.1905	0.2097

^{*}Note: Event counts are rounded to nearest whole number

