For analyses of estimation of incidence rates of the outcomes of interest during follow-up, each analysis will be restricted to patients without a history of outcome of interest prior to the index date (ie baseline period); thus, for each analysis of a given specified outcome, a distinct sub-cohort will be used (i.e. for the estimation of the incidence of hepatitis, only patients with prevalent cases of hepatitis in the baseline period will be excluded from follow-up and will not contribute to person-time at risk).

For each outcome of interest, patients will be followed from the index date to whichever of the following occurs first (follow-up period):

- Occurrence of an outcome of interest,
- 90 days following the discontinuation of IV pantoprazole administration,
- Initiation of a separate IV pantoprazole infusion within 90 days following the discontinuation of IV pantoprazole administration, where a separate infusion is defined as the subsequent administration at least 7 days from the end of the previous infusion,
- Death,
- End of enrollment in the database,
- End of study period (ie, 31 December 2020).

Incidence rates of each prespecified outcome of interest will be estimated as the number of patients with a specific outcome of interest during the follow-up period divided by the total person-time at risk and reported as incidence per 1,000 person-years with associated 95% CIs, assuming a Poisson distribution. Exact Poisson confidence limits for the estimated rate are found as the Poisson means, for distributions with the observed number of events and probabilities relevant to the chosen confidence level, divided by time at risk.

$$egin{aligned} Y_l &= rac{\chi^2_{2Y,\;lpha/2}}{2} \ Y_u &= rac{\chi^2_{2(Y+1),\;1-lpha/2}}{2} \end{aligned}$$

- where Y is the observed number of events, Yl and Yu are lower and upper confidence limits for Y respectively, $\chi 2\nu$, a is the chi-square quantile for upper tail probability on ν degrees of freedom.

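### Section 9.8 defines the chi-square term in its exact Poisson limits by the wrong tail, and the abstract and section 9.8 disagree on when the exact method applies

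*Protocol*

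**What the plan says.** Section 9.8 (Data analysis) has each outcome's rate "reported as incidence per 1,000 person-years with associated 95% CIs, assuming a Poisson distribution". It continues: "Exact Poisson confidence limits for the estimated rate are found as the Poisson means", divided by time at risk. Two formulas follow:

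- Y_l = chi-square(2Y df, subscript alpha/2) / 2
- Y_u = chi-square(2(Y+1) df, subscript 1−alpha/2) / 2

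The note beneath says that Y_l and Y_u "are lower and upper confidence limits for Y respectively", and that the subscripted chi-square term "is the chi-square quantile for upper tail probability". Section 9.8 attaches no event-count condition to these limits.

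The abstract (section 4, Data analysis) gives a different scope: "The CIs will be estimated using the exact method for event counts less than 10, assuming a Poisson distribution". It names no method for counts of 10 or more.

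**The concern.** The printed subscripts and the printed definition cannot both stand. With alpha = 0.05, an upper-tail probability of 0.025 picks a value high in the chi-square distribution, and 0.975 picks one low in it. The formula labelled lower therefore returns a large number and the formula labelled upper a small one.

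The study has no comparator and no a priori hypotheses (section 9.1), so the rates and their confidence intervals are its main quantitative safety result. For an outcome with no events, the upper limit is almost all the information there is. That is also the one count at which the literal rule gives an interval that looks well formed.

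The scope conflict matters because section 9.9 says the protocol will be strictly followed and all analyses will be implemented twice. For counts of 10 or more, one place in the protocol prescribes exact limits and another is silent.

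**Working it through.** **Inputs.** Two-sided 95% level, so alpha/2 = 0.025 and 1−alpha/2 = 0.975 (section 9.8). Formulas, limit labels and tail definition are also from section 9.8. The event counts are illustrative; the protocol prints no Poisson limit to reproduce.

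**Step 1: hand check at Y=0.** Half of a chi-square variable on 2 df is exponential with mean 1.

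- Upper-tail reading: the value with probability 0.975 above it is −ln(0.975) = 0.0253.
- Lower-tail reading: the value with probability 0.975 below it is −ln(0.025) = 3.689.
- Check: a Poisson mean of 3.689 gives zero events with probability exp(−3.689) = 0.025, as an exact upper limit must.
- Ratio: 3.689 / 0.0253 is about 146.

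The lower limit is 0 by convention under both readings, so nothing is inverted.

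**Step 2: both readings at other counts** (events, before dividing by time at risk).

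| Y | Upper-tail, as worded: lower, upper | Lower-tail: lower, upper |
|---|---|---|
| 1 | 3.689, 0.242 | 0.025, 5.572 |
| 5 | 10.242, 2.202 | 1.623, 11.668 |
| 9 | 15.763, 4.795 | 4.115, 17.085 |
| 10 | 17.085, 5.491 | 4.795, 18.390 |
| 75 | 92.90, 59.88 | 58.99, 94.01 |

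Under the wording as printed, the lower limit exceeded the upper at every count tested from 1 to 19,999.

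**Step 3: confirm which reading is exact.** At each lower-tail pair tabulated, the Poisson probability of Y or more events at the lower limit is 0.025, and so is the probability of Y or fewer events at the upper limit. The formulas are therefore the standard exact limits once the quantile is read as cumulative. Keeping the upper-tail definition and exchanging the two subscripts gives identical numbers, because the upper-tail 0.975 point is the lower-tail 0.025 point.

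**Step 4: scope.**

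| Event count | Abstract | Section 9.8 |
|---|---|---|
| Below 10 | exact | exact |
| 10 or more | no method named | exact |

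The size of any difference depends on what an implementer would use at 10 or more, which the protocol does not say. Two assumed alternatives show the range at Y=10, against exact limits of 4.80 to 18.39: a Wald interval gives 3.80 to 16.20 and a log-scale interval 5.38 to 18.59.

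**Step 5: is any printed figure affected?** The only printed intervals are in Table 5 (section 9.6), which uses the Wilson score method. All 12 rows reproduce to four decimals from the rounded event counts. Table 5 is untouched by this point.

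**The case against.** The strongest reply is that this is a one-word slip. The formulas are the textbook ones, the text names the method and labels the limits, and any standard exact-Poisson routine returns the correct values. A literal implementation would betray itself at every count of 1 or more. Section 9.9 provides quality-control review, independent double implementation and third-party adjudication of discrepancies. The abstract is a summary, section 9.8 is the full method, and detail is left to the statistical analysis plan.

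Most of this stands, and it limits the seriousness. It does not make the text right. The protocol chose to print a formula with a definition, and the two conflict. Inversion gives no warning at Y=0. Adjudication would settle a disagreement between teams but would not correct the document, and an analysis plan that is not shown cannot be relied on to do so.

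A reader might infer more than the documents support:

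- *That reported intervals will be wrong.* Nothing shows that the literal rule will be programmed.
- *That the formula is beyond simple repair because exchanging the computed limits leaves the degrees of freedom misplaced.* It does leave them misplaced (at Y=1 the exchange gives 0.242 to 3.689 against 0.025 to 5.572), but the protocol proposes no such exchange. Exchanging the subscripts repairs the formula fully.
- *That most outcomes will have a handful of events.* Low counts are plausible for the rare skin and blood outcomes in small subgroups, but the protocol gives no expected counts, and the smallest in Table 5 are 13 and 15.
- *That counts of 10 or more would get a Wald interval.* The protocol names none.

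**Conclusion.** The point holds as an error in a stated analysis rule. As worded, section 9.8 puts the lower limit above the upper for any count of 1 or more and understates the zero-event upper limit by a factor of about 146 (0.025 against 3.69 events). These figures need no assumption beyond the 95% level and a literal reading. They are on the event scale; a figure per 1,000 person-years would need total follow-up time, which the protocol does not give.

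The scope conflict is also real: two current passages state different conditions for the same interval. Its numerical effect is undetermined, and at Y=10 looks modest under the two assumed alternatives.

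This should be corrected, but it does not threaten the study. The formula is sound apart from its definition, and routine software would give the right limits.

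**What to change.** In section 9.8, define the chi-square term as the lower-tail (cumulative) quantile. Equivalently, keep the upper-tail definition and exchange the two subscripts, but do not do both. State that the lower limit is 0 when Y=0. A worked check would help both implementing teams: Y=5 gives 1.62 to 11.67 events.

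Reconcile the abstract with section 9.8. The simplest way is to delete the abstract's condition on event counts below 10, so that exact limits apply to all counts. If the sponsor wants a threshold, state it in both places and name the method for 10 or more events.

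The cost is a few words in two sections, with no effect on data or on the choice of software.

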Within each study cohort (ie, infants aged 1 month to <1 year and in patients aged 1 to <2 years), the primary study objective is:

Version 2.0, 10 February 2022

(1) to estimate the incidence of prespecified outcomes of interest as described below under variables in patients with a diagnosis of GERD with or without EE and treated with IV pantoprazole.

The two secondary objectives are as follows: (1) to estimate the incidence of prespecified outcomes of interest in patients treated with IV pantoprazole without a diagnosis of GERD or EE, and (2) to provide the frequency of the 25 most common diagnostic codes occurring within 30 days prior to or on the date of initiation of IV pantoprazole through 90 days of the last treatment with IV pantoprazole in patients with a diagnosis of GERD (regardless of EE diagnosis).

Study design

Retrospective cohort study using Optum's longitudinal electronic health records (EHR) repository from the United States (US).

Study population

Two separate cohorts, ie, infants aged 1 month to <1 year and patients aged 1 to <2 years who received at least one administration of IV pantoprazole during a study period of 01 January 2007 to 31 December 2020 and those enrolled in the database for at least 30 days prior to the date of first administration of IV pantoprazole will be identified from the Optum's longitudinal EHR repository. In both cohorts, patients with International Classification of Diseases, Ninth Revision, Clinical Modification (ICD-9-CM) or International Classification of Diseases Tenth Revision, Clinical Modification (ICD-10-CM) codes indicating a preterm birth will be excluded. Within each cohort, 3 subgroups will be identified: (1) patients with ICD-9-CM or ICD-10-CM codes for GERD with EE, (2) patients with ICD-9-CM or ICD-10-CM codes for GERD but without EE, and (3) patients without diagnosis codes for GERD or EE.

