8. RESEARCH QUESTION AND OBJECTIVES

Research Question: What are the incidence rates of potential safety events of interest in infants aged 1 month to <1 year and in patients aged 1 to <2 years who were treated with IV pantoprazole in the real-world setting?

Primary Objective: To estimate the incidence of the following outcomes of interest in infants aged 1 month to <1 year and patients aged 1 to <2 years with a diagnosis of GERD with or without EE and treated with IV pantoprazole:

- Agranulocytosis
- Thrombocytopenia
- Leukopenia
- Pancytopenia
- Hypersensitivity (including anaphylactic reactions and anaphylactic shock)
- Hyperlipidaemia
- Hypertriglyceridemia
- Hyponatraemia
- Hypomagnesaemia
- Hypocalcaemia
- Hypokalaemia
- Diarrhea
- Vomiting
- Abdominal distension
- Hepatobiliary injury
- Urticaria
- Angioedema
- Stevens-Johnson syndrome
- Lyell syndrome
- Erythema multiforme
- DRESS
- Tubulointerstitial nephritis
- Photosensitivity
- Peripheral edema
- Injection site thrombophlebitis

Secondary Objective 1: To estimate the incidence of the above-mentioned outcomes of interest in infants aged 1 month to <1 year and patients aged 1 to <2 years treated with IV pantoprazole without a diagnosis of GERD or EE.

Secondary Objective 2: To provide the frequency of the 25 most common diagnostic codes occurring within 30 days prior to starting or on the date of start of IV pantoprazole (ie, index date) through 90 days of the last treatment with IV pantoprazole among infants aged 1 month

090177e1996138d1\Approved\Approved On: 23-Feb-2022 16:44 (GMT)

to <1 year and patients aged 1 to <2 years with a diagnosis of GERD (regardless of EE diagnosis).

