9. RESEARCH METHODS

9.1. Study design

This will be a retrospective cohort study with no comparator group. No a priori hypotheses are specified. Descriptive analyses including an estimation of incidence rates will be performed.

9.2. **Setting**

The study will be conducted using Optum's longitudinal integrated EHR from the US¹, which is described in Section 9.5 This data source includes data from adjudicated administrative insurance claims, inpatient electronic health records, as well as outpatient EHR enabling capture of exposure to IV pantoprazole in the study population of interest. The study period will be defined from 01 January 2007 to 31 December 2020.

9.3. **Study population**

Two separate cohorts, ie, infants aged 1 month to <1 year and patients aged 1 to <2 years will be identified during the study period using the following inclusion and exclusion criteria.

9.3.1. **Inclusion criteria**

Patients must meet all of the following inclusion criteria to be eligible for inclusion in the study:

- 1. At least one administration of IV pantoprazole during the study period from January 1, 2007 to December 31, 2020, and
- 2. For the cohort of infants aged 1 month to <1 year (Cohort 1): Age 1 month to <1 year on the index date (ie, the date of first administration of IV pantoprazole); For the cohort of patients aged 1 to <2 years (Cohort 2): Age 1 to <2 years on the index date.
- 3. Patients must be enrolled in the database for at least 30 days prior to the index date

In addition to this 30-day lookback window, patients will be further excluded based on the occurrence of a history of outcomes of interest identified in Table 3 occurring prior to the index date.

9.3.2. **Exclusion criteria**

Patients meeting any of the following criteria will not be included in the study:

1. Patients with any of the following ICD-9-CM or ICD-10-CM codes occurring prior to or on the index date indicating a preterm birth or birth weight less than 2.36 kilograms will be excluded:

ICD-9-CM codes: 765.01-765.08; 765.10-765.19; 765.21-765.28

ICD-10-CM codes: P07.21-P07.26; P030-P039; P07.01-P07.03; P07.14-P07.18

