The cut-off of birth weight less than 2.36 kilograms is defined based on a birth weight that is less than third percentile weight for males at birth obtained from Centers for Disease Control and Prevention (CDC) infant weight-for-age charts (available at URL: https://www.cdc.gov/growthcharts/html charts/wtageinf.htm). It is reasonable to assume that infants with birth weight less than 2.36 kilograms are most likely born preterm.

9.3.3. **Subgroups**

Within each cohort (ie, Cohort 1 and 2), 3 subgroups will be identified as follows:

- (1) Patients who have a diagnosis of GERD with EE: defined based on the presence of at least one of the ICD-9-CM or ICD-10-CM codes as shown in Table 1 and the presence of an additional ICD-9-CM or ICD-10-CM code for ulcer of the esophagus during the baseline period or on the index date, as shown in Table 1.
- (2) Patients who have a diagnosis of GERD without EE: defined based on the presence of at least one of the ICD-9-CM or ICD-10-CM codes and no ICD-9-CM or ICD-10-CM code for ulcer of esophagus during the baseline period or on the index date, as shown in Table 1.
- (3) Patients without a diagnosis of GERD or EE: defined as patients who do not have any of the ICD-9-CM or ICD-10-CM codes as shown in Table 1 during the baseline period or on the index date.

ICD-9-CM codes will be used to identify the subgroups prior to October 2015, after which ICD-10-CM codes will be used. No validated algorithm for GERD with or without EE were found to be available via literature review, therefore, a combination of clinical input, and the available codes identified in the literature will be used.² Additionally, there is no explicit ICD-9-CM code for GERD with/without esophagitis. Therefore, based on a cross-sectional study that examined the validity of diagnosis codes of benign upper gastrointestinal disorders using electronic patient records², and an online conversion tool maintained by the Center for Medicare Services and the Centers for Disease Control and Prevention (available at URL: https://icd.codes/convert/icd10-to-icd9-cm), the subgroups of GERD with or without EE will be determined using the operational definitions shown in Table 1:

Table 1. Operationalization of subgroups

Subgroup	ICD-10- CM Code	Description of ICD- 10-CM code	ICD-9- CM Code	Description of ICD-9- CM code

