9.7. Data management

De-identified Optum EHR data will be analyzed using the Aetion Evidence Platform (AEP). Data to be used for the proposed analysis have already been linked and uploaded into the AEP. The AEP is a data-handling technology, which allows for the analysis of large patient datasets by indexing patient data into a form that can be queried by an internal patient variable language and has been previously used.^{3,4,5} Data are minimally transformed at the point of connection to the AEP, thus the original format of the raw Optum EHR data is preserved. At the point of data connection to the platform some discard rules are applied. Patient events are excluded if patient identification (ID) is missing and if the "start of enrollment" date is preceded by the "end of enrollment" date in the original data. Additionally, patient events are excluded if there are no dates associated with them, or if the start date of the event is preceded by the end date of the event (e.g. discharge date precedes admission date for an inpatient event). Action IDs are assigned to Optum EHR patient IDs and a crosswalk file is kept as a protected file available upon request to authorized parties. The data are at the individual patient level and will be analyzed within the AEP.

9.8. **Data analysis**

090177e1996138d1\Approved\Approved On: 23-Feb-2022 16:44 (GMT)

All statistical analysis will be performed in the two cohorts of interest, ie, infants aged 1 month to < 1 year and patients aged 1 to < 2 years, separately using the AEP version 4.2. Analysis combining the two cohorts of interest will not be performed.

Descriptive statistics will be presented for key variables of interest i.e., demographic characteristics, comorbidities and duration and dose of IV pantoprazole, listed in Section 9.4.3 to characterize the overall cohort treated with IV pantoprazole and in the 3 subgroups defined based on the presence or absence of GERD and EE and listed under Section 9.3.3. These will include counts and percentages for categorical data and statistics such as mean, median, standard deviation, and range for continuous variables.

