For the analysis of the primary objective, incidence rates for all outcomes of interest will be estimated in the overall cohort and in the 2 subgroups, i.e., patients with GERD and EE and patients with GERD, but without EE. Within the overall cohort and in the 2 subgroups, incidence rates will be calculated by duration of IV pantoprazole treatment (<4 days, ≥ 4 days). For the analysis of the secondary objective 1, incidence rates will be estimated for the subgroup of patients treated with IV pantoprazole without a diagnosis of GERD or EE in each cohort and by duration of IV pantoprazole treatment (<4 days, ≥ 4 days) within each cohort. For the analysis of the secondary objective 2, counts of the 25 most common diagnostic codes occurring within 30 days prior to starting or on the date of start of IV pantoprazole (ie, index date) through 90 days of discontinuation with IV pantoprazole in the subsets of patients with a diagnosis of GERD with or without EE will be generated. For each patient, reoccurring codes within 30 days prior to starting or on the date of start of IV pantoprazole (ie, index date) and through 90 days of discontinuation with IV pantoprazole will be counted once.

Detailed methodology for summary and statistical analyses of data collected in this study will be documented in a statistical analysis plan (SAP), which will be dated, filed and maintained

by the sponsor. The SAP may modify the plans outlined in the protocol; any major modifications of primary endpoint definitions or their analyses would be reflected in a protocol amendment.

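### Section 9.8 does not prespecify the combined GERD rate that the primary objective names, and it places the overall treated cohort, including patients without GERD, under that objective

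*Protocol*

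**What the plan says.** The primary objective has the same population on the title page, in the abstract and in section 8. The abstract words it as incidence "in patients with a diagnosis of GERD with or without EE and treated with IV pantoprazole", within each of the two age cohorts. Secondary objective 1 covers treated patients with neither diagnosis.

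Section 9.8 then assigns populations to objectives. For the primary objective, "incidence rates for all outcomes of interest will be estimated in the overall cohort and in the 2 subgroups", and it identifies the two subgroups as GERD with EE and GERD without EE. The split by treatment duration (<4 days, ≥4 days) is run in the same three populations. The no-GERD/EE subgroup is assigned to secondary objective 1.

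The overall cohort is not limited to GERD. Section 9.3.1 requires "At least one administration of IV pantoprazole during the study period from January 1, 2007 to December 31, 2020", plus age and 30 days of enrolment. Section 9.8 plans descriptive statistics "to characterize the overall cohort treated with IV pantoprazole and in the 3 subgroups", and the third of these subgroups in section 9.3.3 is "Patients without a diagnosis of GERD or EE: defined as patients who do not have any of the" listed GERD and EE codes.

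Section 9.6 gives 7,489 infants and "6,657 patients aged 1 to <2 years who have been treated with IV pantoprazole will be eligible for inclusion in the study". Table 5 gives Wilson intervals for those two totals. The protocol states no expected number of GERD patients.

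**The concern.** The primary objective describes one population per age cohort: treated patients with GERD, whatever their EE status. Of the three populations that section 9.8 lists for it, one is wider than the objective (the overall cohort) and two are parts of it (the EE subgroups). The population itself is not listed.

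Two consequences follow. A rate reported under the primary objective will include patients whom the protocol places under a secondary objective, and the duration split inherits the same mixture. The two rates that do stay inside the GERD population depend on EE coding. Section 9.10 concedes that patients with EE may be counted as without it, because confirmation by endoscopy is often not sought in infants. The combined GERD rate does not depend on that coding, and it is the one not prespecified.

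This is not a detail left to the SAP. The protocol fixes these populations itself, section 9.8 reserves major changes to the primary analyses for a protocol amendment, and section 9.9 says the protocol will be strictly followed.

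**Working it through.** **1. Populations side by side (each age cohort)**

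| Population | In the primary objective? | Planned rate in 9.8 |
|---|---|---|
| GERD with EE (subgroup 1) | part of it | yes, primary |
| GERD without EE (subgroup 2) | part of it | yes, primary |
| Subgroups 1+2 combined | yes, all of it | not specified |
| No GERD or EE (subgroup 3) | no | yes, secondary 1 |
| Overall treated cohort | wider than it | yes, primary |

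The abstract's analysis paragraph lists the overall cohort and the three subgroups, again without a combined GERD row.

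**2. Can the combined rate be recovered?** Under section 9.3.3 and Table 1, subgroup 1 needs a GERD code and an oesophageal ulcer code; subgroup 2 needs a GERD code and no ulcer code. Both are fixed at baseline or the index date. They are therefore disjoint and together contain every GERD-coded patient. With Y events and T person-years,

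rate(GERD) = (Y1 + Y2) / (T1 + T2),

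with the exact Poisson limits of section 9.8 applied to Y1 + Y2.

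Illustration with assumed values (40% of 7,489 have GERD, 5% of those have EE, 0.25 years of follow-up each, about 20 events per 1,000 person-years):
- Person-time: 7,489 × 0.40 × 0.25 = 748.9 person-years, of which EE 37.4 and no EE 711.5.
- EE: 1 event, 95% CI 0.7 to 148.8 per 1,000 person-years.
- No EE: 14 events, 95% CI 10.8 to 33.0.
- Combined: 15 / 748.9 = 20.03 per 1,000 person-years, 95% CI 11.2 to 33.0.

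Moving a patient from EE to no EE changes the first two results and leaves the third unchanged.

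**3. How far can the overall rate lie from the GERD rate?** With g the GERD share of person-time,

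overall rate = g × GERD rate + (1 − g) × non-GERD rate.

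The protocol gives neither g nor any rate, so the values below are assumed, with the non-GERD rate set at 100 per 1,000 person-years:

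| g | GERD rate 50: overall (ratio to GERD) | GERD rate 200: overall (ratio to GERD) |
|---|---|---|
| 20% | 90 (1.80) | 120 (0.60) |
| 40% | 80 (1.60) | 140 (0.70) |
| 60% | 70 (1.40) | 160 (0.80) |
| 80% | 60 (1.20) | 180 (0.90) |

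The ratio is 1 only if the two rates are equal or g is 100%.

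**4. Table 5.** The Wilson 95% interval on rounded events divided by n reproduces all 12 rows to four decimals. For example, 75/7,489 gives 0.0080 to 0.0125 and 67/6,657 gives 0.0079 to 0.0128. The arithmetic is right; the denominators are all treated patients. The same formula at a frequency of 1% in the infant cohort, for assumed GERD shares of patients:

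| GERD share | n | 95% interval |
|---|---|---|
| 100% (Table 5) | 7,489 | 0.80% to 1.25% |
| 50% | 3,744 | 0.73% to 1.37% |
| 25% | 1,872 | 0.64% to 1.56% |
| 10% | 749 | 0.50% to 2.00% |

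The last three rows use the frequency itself, not a rounded event count.

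**The case against.** The best defence is that the objective asks for two estimates, one with EE and one without. The amendment table's reason for the change to section 9.8 describes the primary objective as an analysis in those two subgroups. Secondary objective 2 uses a different phrase for GERD irrespective of EE, which suggests that the authors could have asked for a combined group and did not. This reading is available. It does not explain why the overall cohort stands under the primary objective, and the contrast in wording also shows that the protocol already contemplates a combined GERD group.

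A reader might infer that the objective goes unanswered, with no obtainable estimate or interval. The documents do not support that: step 2 shows that both follow by addition, provided events and person-time are tabulated by subgroup.

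A reader might also infer that the overall rate is to be the headline result. No section ranks it above the subgroup rates, and the no-GERD/EE subgroup is reported separately, so a difference between populations would be visible. The research question itself covers all treated patients, which gives the overall cohort a legitimate place in the report. The study is descriptive, and no test depends on the label.

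Finally, if EE is seldom coded, the planned rate in GERD without EE will lie close to the combined rate. With EE at 2% to 10% of GERD person-time and twice the rate, the combined rate is (1 − e) + 2e = 1 + e, or 1.02 to 1.10 times the rate without EE. These are assumed values too, but the point is fair and lowers the practical stakes.

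**Conclusion.** The point stands as a mismatch between objective and planned analysis, not as a loss of information. The populations that section 9.8 names for the primary objective do not include the one the objective describes, and they do include patients who belong to secondary objective 1. On the two-estimates reading, only the second half of that statement remains.

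The numerical effect cannot be stated. The range of 0.6 to 1.8 for the overall rate relative to the GERD rate rests wholly on an assumed GERD share of 20% to 80% and assumed twofold rate differences. It concerns the overall cohort only; the planned rate in GERD without EE may be much closer. Table 5 is correct and correctly labelled for all treated patients. It simply does not show the precision available for the primary population, which will be lower unless every treated patient has GERD.

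The correction is worth making because it costs almost nothing, aligns the primary estimate with its objective, and gives an estimate unaffected by the EE misclassification conceded in section 9.10.

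**What to change.** In section 9.8 and the abstract, define the primary analysis set in each age cohort as patients with GERD with or without EE (subgroups 1 and 2 combined). Report its rate with the exact Poisson interval and with the <4 / ≥4 day split. Present the two EE subgroups as breakdowns of that set, with events and person-time shown, and label the overall treated cohort as supplementary.

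Secondarily, add rows to Table 5 for the expected number of GERD patients in each age cohort, taken from the feasibility query. Recasting the table as Poisson rates per 1,000 person-years would match the planned estimate but is optional.

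The cost is a wording change in sections 9.6 and 9.8 and the abstract, one extra column in the result tables, and stated precision that is less favourable than the present Table 5. No new data are needed.
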